8.1.3 Dose-Limiting Toxicities

In case of any occurrence of one of the following criteria in one of the cohorts, no further dose escalation will be applied in subsequent cohorts:

- ≥ 1 subject of one cohort reporting grade ≥2 AEs up to FU-V1 (3 days after the last IMP dose)
- Corrected QT interval by Fredericia (QTcF) ≥500 ms and/or an increase of QTcF from baseline of ≥ 60 ms, confirmed by repeated ECGs, in at least 1 subject up to FU-V1 (3 days after the last IMP dose)

NOTE: Only toxicities with a clear-cut alternative explanation will be deemed non-DLT.

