ATL-001 4 mg/kg / Placebo	From 10 mL to 20 mL	10 mL (scale - 0.2)

Date: 13 December 2023

Sponsor: Atlas Molecular Pharma S.L. Study Code: ATL001-PI-CEP

NCT No.: 05647343

The volume to be administered will be extracted from the IMP container and will be deposited in a glass containing approximately 50-100 ml of water and to which 2-4 tablespoons of sugar have been added. The IMP will be stirred with a spoon and drunk in one gulp, if possible.

For each cohort, subjects will be screened up to 30 days prior to the Baseline visit. All eligible subjects will be admitted to the study site on Day 1 (Baseline), for baseline assessments and to confirm their eligibility. They will remain domiciled until discharged on Day 2, after completion of the assessments and after receiving the IMP. All screening safety evaluation results must be available prior to dosing. Subjects will be randomized immediately prior to Day 1 IMP administration. At Day 5, subjects will be admitted again to the study site, where they will remain domiciled until discharged on Day 6 after completion of the assessments. Subjects will return to the study site 3 days after their last IMP dose and 30 days after last IMP dose to undergo safety follow-up evaluations.

For each cohort, the subjects will be randomized to receive ATL-001 (6 subjects/cohort) or to receive placebo (2 subjects/cohort). Each cohort will be sub-divided into 2 sub-cohorts (Figure 1):

- The first sub-cohort will have 2 sentinel subjects: one will be randomized to receive ATL-001 and one to receive placebo. Once these subjects complete their follow-up visit 1 (FU-V1) (3 days after the last IMP dose), the Sponsor and Principal Investigator (PI) will review all the available safety and tolerability data before deciding the inclusion of the remaining 6 subjects in the second sub-cohort.
- The second sub-cohort will include 6 additional subjects simultaneously: 5 randomized subjects to receive ATL-001 and 1 to receive placebo. Upon availability of the FU-V1 (3 days after the last IMP dose) data of all subjects, the Data and Safety Monitoring Board (DSMB) will review all available safety, tolerability, and will issue a recommendation for the next cohort to start (Section 8.1.1). Only then the study may proceed with the next cohort for treatment administration after Sponsor decision. The same procedure will be followed for each subsequent cohort.

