8.1.1 Data and Safety Monitoring Board Evaluation

The DSMB will issue recommendations regarding proceeding to each subsequent cohort based on all available safety, tolerability from all prior cohorts. The stopping rules described in Section 8.1.2 and the DLTs described in Section 8.1.3 will be considered.

Additionally, if the study level stopping rules described in Section 8.1.2 are met, the DSMB will automatically meet and issue a recommendation. The final decision on these actions will be taken by the Sponsor. The DSMB may meet additional times at the request of the PI or the Sponsor.

The DSMB may issue the following recommendations:

- To recommend the dosing start for the next cohort
- To change the dose for the next cohort*
- To repeat a dose that has been previously studied
- To change the administration schedule
- To add or change the timing of safety and/or PK assessments
- To recommend to the Sponsor that dosing should be stopped

^A After sentinel subjects complete FU-V1 (3 days after the last IMP dose)

^B Upon availability of the FU-V1 (3 days after the last IMP dose) data of all the cohort subjects. Final decision will be taken by the Sponsor based on DSMB recommendation

^{*}The DSMB proposed ATL-001 dose for a given cohort should not be superior to 8.1 mg/kg (see Appendix 1).

Date: 13 December 2023

Sponsor: Atlas Molecular Pharma S.L. Study Code: ATL001-PI-CEP

NCT No.: 05647343

A DSMB charter will be produced by the Sponsor and will contain the following details:

- Committee members and requirements for quorum
- Data review requirements
- Process for informing the IRB and RA of any safety concerns, if appropriate
- Process for requesting additional pertinent information from the investigators
- Process for informing the investigators (and IRB/RA, if appropriate) of any decisions derived from the recommendations of the DSMB

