8.1.2 Study-Level Stopping Rules

In case of any occurrence of one of the following criteria in one of the cohorts, the IMP administration will be temporarily stopped and the DSMB will meet to review the safety and tolerability data and issue a recommendation:

- 1 serious AE (SAE) in one subject that is considered to be at least possibly related to the IMP
- ≥2 subjects of one cohort (or 1 out of 2 sentinel subjects) reporting grade ≥2 or higher AEs that are considered to be at least possibly related to the IMP, regardless of attribution or relatedness to further enhance safety in this healthy volunteer study

If, after stopping the study, the Sponsor deem it appropriate to restart the study following a safety review by the DSMB, this will be done following approval of a substantial protocol amendment.

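### Section 8.1.2 has no QTcF trigger, so a confirmed QTcF dose-limiting toxicity in one non-sentinel subject need not pause dosing or convene the DSMB

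*Protocol*

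**What the plan says.** Protocol 8.1.3 lists two kinds of dose-limiting toxicity (DLT). One is a grade 2 or higher AE in at least one subject of a cohort. The other is a QTcF of at least 500 ms and/or a rise of at least 60 ms from baseline, "confirmed by repeated ECGs, in at least 1 subject up to FU-V1". For both, the only stated action is that "no further dose escalation will be applied in subsequent cohorts".

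Protocol 8.1.2 is the section that stops IMP administration temporarily and calls the DSMB. It has two triggers. The first is one SAE at least possibly related to the IMP. The second is two or more "subjects of one cohort (or 1 out of 2 sentinel subjects) reporting grade" 2 or higher AEs. If the Sponsor restarts after such a stop, "this will be done following approval of a substantial protocol amendment".

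Protocol 8.1.1 links the two sections to the DSMB differently. When the board advises on the next cohort, "the DLTs described in Section 8.1.3 will be considered". The unscheduled meeting depends on 8.1.2 alone: "if the study level stopping rules described in Section 8.1.2 are met, the DSMB will automatically meet and issue a recommendation". Beyond that, "The DSMB may meet additional times at the request of the PI or the Sponsor".

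For the two sentinels, Protocol 8.1 says the Sponsor and PI "will review all the available safety and tolerability data before deciding the inclusion of the remaining 6 subjects". The routine DSMB review follows once FU-V1 data are in for all subjects of the cohort, three days or more after the last dose.

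**The concern.** The protocol regards one confirmed QTcF event as serious enough to rule out any higher dose. It attaches no rule to the dose then being given. Whether the remaining subjects keep receiving that dose, and whether the DSMB hears of the event before they do, depends on how the event is classified and on decisions left to the Investigator, PI and Sponsor.

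This matters most in Cohort 5. Section 13.4 says Cohort 4 was complete and analysed before Cohort 5 enrolled, and 4 mg/kg is the highest planned dose. The DSMB could still propose a further dose under 8.1.1, but no later cohort is planned. The one mandated consequence of a QTcF DLT would then change nothing for anyone being dosed. In a first-in-human study in healthy volunteers, a rule is preferable to discretion.

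**Working it through.** The plan states no operating characteristic for its safety rules, so there is no figure to reproduce. The check is a comparison of rules followed by a dose count.

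**Which events reach 8.1.2**

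| Event | 8.1.3: escalation ends | 8.1.2: pause and DSMB meeting |
|---|---|---|
| Grade 2 or higher AE, one non-sentinel, not a related SAE | Yes | No |
| Grade 2 or higher AE, one sentinel | Yes | Yes |
| Grade 2 or higher AEs, two subjects | Yes | Yes |
| Possibly related SAE, any subject | As graded | Yes |
| Confirmed QTcF DLT, one non-sentinel | Yes | Only if judged a possibly related SAE, or if recorded as a grade 2 or higher AE and a second subject also has one |
| Confirmed QTcF DLT, one sentinel | Yes | Only if recorded as a grade 2 or higher AE or a possibly related SAE |

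AEs therefore have a two-tier scheme: one subject ends escalation, and two subjects or one sentinel pause dosing. QTcF appears in the first tier only. It reaches the second by being recorded as a qualifying AE or SAE. Grading follows CTCAE (12.1.1), but the documents do not say which grade these QTcF values carry. For one non-sentinel this makes no difference, because the AE trigger needs two subjects whatever the grade.

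**Doses left in the second sub-cohort**

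Inputs:
- five daily doses (10.3)
- six subjects, five active and one placebo (8.1)
- post-dose ECGs at 2 h on Day 1, 24 h on Day 2, 2 h on Day 5, 24 h on Day 6, and FU-V1 (8.2.1)

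Assumptions: all six start on the same day, and the affected subject is on active drug. Sections 8.2.1.2.1.2 and 10.3 disagree on whether the Day 2 dose follows or precedes that day's assessments, so both are shown.

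Doses left = subjects × doses not yet given.

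| ECG at which the event is first seen | Doses left per subject | All six | Active | Active, affected subject withdrawn |
|---|---|---|---|---|
| Day 1, 2 h | 5 − 1 = 4 | 6 × 4 = 24 | 5 × 4 = 20 | 4 × 4 = 16 |
| Day 2, dose after assessments | 4 | 6 × 4 = 24 | 5 × 4 = 20 | 4 × 4 = 16 |
| Day 2, dose before assessments | 3 | 6 × 3 = 18 | 5 × 3 = 15 | 4 × 3 = 12 |
| Day 5, Day 6 or FU-V1 | 0 | 0 | 0 | 0 |

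In the Day 1 and Day 2 rows, two of each subject's remaining doses (Days 3 and 4) are taken at home with no site visit. Time taken to confirm the finding by repeat ECG is not counted, because the protocol does not give it.

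**When the DSMB would otherwise see it**

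FU-V1 falls on Day 5 + 3 = Day 8. The scheduled review therefore comes at least 8 − 1 = 7 days after a Day 1 event, when that cohort's dosing is over.

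**The case against.** The strongest reply is that the tiers are deliberate. One non-sentinel with any grade 2 AE also ends escalation without a pause, and section 1.1 records that the DLT and stopping criteria were revised together after FDA suggestions. That stands: the single-subject gap is not peculiar to QTcF. It does not explain why QTcF has no pause tier at all. As written, even several confirmed QTcF DLTs would not meet 8.1.2 unless they were also recorded as qualifying AEs or SAEs.

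The second reply is the seriousness definition. Section 12.1.4 asks for medical judgement and counts as serious an important event that may jeopardize the subject or need intervention. A confirmed QTcF of 500 ms or more is a natural candidate. If it is also judged possibly related, 8.1.2 applies in any subject. This narrows the gap, but it leaves the outcome to a classification.

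Third, other safeguards exist. The Investigator may withdraw the subject from treatment (9.4.2), the PI may stop the study (8.5), and the PI or Sponsor may call the DSMB. The DSMB charter, which the documents do not include, may add more. The safeguards in the protocol are all discretionary, and 9.4.2 names no QTcF criterion.

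Fourth, risk is not shown. The only identified risk is gastrointestinal (6.5), clinically significant QTc prolongation is excluded at entry (9.3), and no QT signal is reported. This limits the weight of the point.

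**Conclusion.** The concern holds in a limited form. One non-sentinel subject with a confirmed QTcF DLT mandates neither a pause nor a DSMB meeting, unless the event is judged a possibly related SAE or a second subject in the cohort has a grade 2 or higher AE. The doses affected range from 0 to 24 in the second sub-cohort, depending on when the event is first seen. The upper end needs an event on Day 1, or on Day 2 before dosing. The range rests on a same-day start; with staggered starts, even a late event in one subject could leave doses for others. No probability is attached, because the documents give no rate.

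Three stronger readings are not supported.
- A reader might infer that a QTcF DLT never pauses dosing or never reaches the DSMB. It can do so through the SAE or AE triggers, and the board considers DLTs at its scheduled review.
- A reader might infer an equal gap for sentinels. A sentinel event recorded as a grade 2 or higher AE already triggers 8.1.2, and the Sponsor and PI must review sentinel data before the other six are included. That review is not a DSMB meeting, but the sentinel case is secondary.
- A reader might take section 12.2, which restricts reporting of asymptomatic laboratory and vital-sign findings and does not mention ECG, to mean that ECG findings escape AE recording. The restriction simply does not cover them, so they fall under the broad AE definition in 12.1.1.

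This is a worthwhile change at low cost, and it should be made.

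**What to change.** Add a third trigger to 8.1.2 using the sponsor's own threshold: QTcF of at least 500 ms and/or a rise of at least 60 ms from baseline, confirmed by repeat ECGs, in one or more subjects. Dosing then pauses, and the automatic DSMB meeting in 8.1.1 follows without further change.

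Add one sentence on restart. If the QTcF criterion is the only 8.1.2 criterion met and the DSMB clears the event, no substantial amendment is needed. If the event is also a possibly related SAE, or meets the grade 2 AE rule, the present amendment requirement stays. Without that limit, the exemption could weaken protection that exists now.

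The cost is one protocol amendment submitted to the IRB and regulatory authority (14.1.1), a matching line in the DSMB charter, and possibly one ad hoc DSMB meeting with a short delay. The requirement for confirmation by repeat ECG already limits false alarms.

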8.2 Study Procedures

8.2.1 Schedule of Study Events

The study assessments described in the sections below are presented in detail in Section 11.2 (PK assessments), Section 11.3 (demographic data and baseline characteristics) and Section 11.4 (safety assessments). Recording and reporting of AEs are described in detail in Section 12.

The timing of all study events is shown in Table 1.

The following points must be noted:

- If different assessments are scheduled for the same nominal time, then the assessments should occur in the following order whenever possible:
 - 1. 12-lead ECG and vital signs
 - 2. Blood draw
- The timing and number of planned study assessments, including safety or PK assessments may be altered during the course of the study based on newly available data (e.g., data from preceding cohorts) after DSMB recommendation (see Section 8.1.1).
- Any change in the timing or the addition of time points for any planned study assessment must be documented in a Note to File, which must be approved by the relevant Sponsor study team member and will be archived in the study Sponsor and site study files. This will not constitute a protocol amendment.

The day of the first administration of the IMP will be considered Day 1 of the study.

Version: 4.0

Date: 13 December 2023

Sponsor: Atlas Molecular Pharma S.L. Study Code: ATL001-PI-CEP

NCT No.: 05647343

8.2.1.1 Screening Visit (Day -30 to Day -1)

At the Screening Visit, the following activities and assessments will be performed:

- Informed consent signature
- Assessment of inclusion/exclusion criteria
- Demographic data
- Medical history
- Physical examination
- Vital signs, including blood pressure, pulse rate and body temperature
- Laboratory safety assessments, including hematology, biochemistry and urinalysis
- Viral serology, comprising human immunodeficiency virus (HIV) I and II, HbsAg, hepatitis C virus and coronavirus disease (COVID)-19 polymerase chain reaction (PCR) testing
- Drug of abuse and alcohol screen
- Serum pregnancy test (for female subjects of childbearing potential only)
- ECG
- Concomitant medications
- AEs (pre-treatment-emergent events)

8.2.1.2 Treatment Period

After the Screening visit and confirmation of full eligibility, the subjects will receive the IMP once daily for 5 days. The first and last administration of the IMP (Day 1 and Day 5) will be performed at the hospital. At Day 2, prior to hospital discharge, the subject will be administered with the IMP. The other days (Day 3 to Day 4), treatment will be self-administered at home. During the first hospital admission (Day 1 to Day 2), subjects will be provided with the IMP to be administered daily from Day 3 to Day 4 and they will receive detailed instructions (see above, Section 8.1) on how to properly take and storage the medication. After the first and last administration of the IMP (Day 1 and Day 5) all subjects will be hospitalized for 24 hours. Subjects will be discharged at Day 2 and Day 6 after completing their assessments.

The timing of all study visits during this period is shown in Table 1.

8.2.1.2.1 Hospital admission (Day 1 to Day 2)

8.2.1.2.1.1 Day 1 (Baseline)

At Day 1 (Baseline), the following activities and assessments will be performed prior to IMP administration:

- Assessment of changes in inclusion/exclusion criteria
- Randomization
- Assessment of changes in the medical history
- Physical examination
- Vital signs, including blood pressure, pulse rate and body temperature
- Laboratory safety assessments, including hematology, biochemistry and urinalysis
- Drug of abuse and alcohol screen
- Urine pregnancy test (for female subjects of childbearing potential only)
- ECG
- PK blood sampling (0 min or pre-dose).

Version: 4.0

Date: 13 December 2023 NCT No.: 05647343

Concomitant medications

AEs (pre-treatment-emergent events)

After performing all the previous assessments, the IMP will be administered and the subjects will remain in the hospital for 24 hours. During Day 1, the following additional activities and assessments will be performed:

Sponsor: Atlas Molecular Pharma S.L.

Study Code: ATL001-PI-CEP

- Physical examination (2 hours after the first IMP dose)
- Vital signs, including blood pressure, pulse rate and body temperature (2 hours after the first IMP dose)
- Laboratory safety assessments, including hematology, biochemistry and urinalysis (2 hours after the first IMP dose)
- ECG (2 hours after the first IMP dose)
- PK blood sampling (15 min, 30 min, 1 hour, 1:30 hours, 2 hours, 2:30 hours, 3 hours, 4 hours, 6 hours, 8 hours and 12 hours after the first IMP dose)
- Concomitant medications
- AEs

8.2.1.2.1.2 Day 2

Subjects will be discharged at Day 2 after completing their assessments and after receiving the IMP. At Day 2 (24 hours after the first IMP dose), the following activities and assessments will be performed:

- Physical examination
- Vital signs, including blood pressure, pulse rate and body temperature
- Laboratory safety assessments, including hematology, biochemistry and urinalysis
- ECG
- PK blood sampling
- Concomitant medications
- AEs

Prior to hospital discharge (and after the performance of the activities and assessments listed above), the subjects will be administered with the IMP.

8.2.1.2.1.3 Day 3 to Day 4

Treatment will be self-administered at home once daily following the investigator instructions. No site visits are planned from Day 3 to Day 4. During this period of time, subjects will record daily AEs and IMP administrations in the subject diary.

8.2.1.2.2 Hospital admission (Day 5 to Day 6)

8.2.1.2.2.1 Day 5

At Day 5, the following activities and assessments will be performed prior to IMP administration:

- Urine pregnancy test (for female subjects of childbearing potential only)
- PK blood sampling (0 min or pre-dose)

After performing all the previous assessments, the IMP will be administered, and the subjects will remain in the hospital for 24 hours. During Day 5, the following activities and assessments will be performed after IMP administration:

- Physical examination (2 hours after the last IMP dose)
- Vital signs, including blood pressure, pulse rate and body temperature (2 hours after the last IMP dose)

Version: 4.0

Date: 13 December 2023

Sponsor: Atlas Molecular Pharma S.L. Study Code: ATL001-PI-CEP

NCT No.: 05647343

• Laboratory safety assessments, including hematology, biochemistry and urinalysis (2 hours after the last IMP dose)

- ECG (2 hours after the last IMP dose)
- PK blood sampling (15 min, 30 min, 1 hour, 1:30 hours, 2 hours, 2:30 hours, 3 hours, 4 hours, 6 hours, 8 hours and 12 hours after the last IMP dose)
- Concomitant medications
- AEs

8.2.1.2.2.2 Day 6

Subjects will be discharged at Day 6 after completing their assessments. At Day 6 (24 hours after the last IMP dose), the following activities and assessments will be performed:

- Physical examination
- Vital signs, including blood pressure, pulse rate and body temperature
- Laboratory safety assessments, including hematology, biochemistry and urinalysis
- ECG
- PK blood sampling
- · Concomitant medications
- AEs

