- ⁶ Pregnancy testing of female subjects only. At screening pregnancy test will be done with using the blood sample; urine pregnancy test will be done on admission.
- ⁷ Also pre-dose at Day 5
- ⁸ Adverse events will be daily recorded by the subject in the subject diary and will not involve visit to the hospital.
- ⁹ Pre-treatment-emergent events.

CONFIDENTIAL

Date: 13 December 2023

Sponsor: Atlas Molecular Pharma S.L. Study Code: ATL001-PI-CEP NCT No.: 05647343

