10.3 Dose and Treatment Regimens in the Study

The IMPs will be administered orally once daily for 5 days (i.e., total of 5 administrations of IMP). On the morning of Day 1 to Day 5, each subject will receive a single oral dose of ATL-001 or placebo administered under fasting conditions as described above (Section 8.1). Subjects will fast overnight (at least 10 hours) prior to be dosed at approximately the same time on the morning of Day 1 through Day 5.

The first and last administration of the IMP (Day 1 and Day 5) will be performed at the hospital. At Day 2, prior to all clinical activities and assessments and to hospital discharge, the subject will be administered with the IMP. The other days (Day 3 to Day 4), treatment will be self-administered at home. During the first hospital admission (Day 1 to Day 2), subjects will be provided with the IMP to be administered daily from Day 3 to Day 4 and they will receive detailed instructions on how to properly take and storage the medication.

The starting dose in the Cohort 1 will be 0.2 mg/kg of ATL-001 or placebo. The doses in Cohort 2, Cohort 3, Cohort 4 and Cohort 5 are planned to be 0.5 mg/kg, 1 mg/kg, 2 mg/kg and 4 mg/kg of ATL-001 or placebo. These doses were selected based on pre-clinical data. Dose selection rationale is detailed in Section 6.3. ATL-001 dose to be administered from Day 1 to Day 5 should be calculated based on the subject's weight assessed at Screening visit.

Upon consideration of all the available safety and tolerability data from all cohorts tested to date, the DSMB will provide recommendation for the progression to the next cohort or may recommend an

Date: 13 December 2023

Sponsor: Atlas Molecular Pharma S.L. Study Code: ATL001-PI-CEP

NCT No.: 05647343

additional procedure to be taken (i.e., to test a different IMP dose or administration schedule), as outlined in Section 8.1.1.

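### No scheduled adverse event review feeds the Section 8.1.2 pause between Day 2 discharge and the Day 5 dose, and on Day 5 the listed review follows dosing

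*Protocol*

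**What the plan says.** **The pause.** Under Protocol Section 8.1.2, once a criterion occurs in a cohort, "the IMP administration will be temporarily stopped and the DSMB will meet to review the safety and tolerability data". The criteria are one serious AE judged possibly related or more, or AEs of grade 2 or higher in at least two subjects of the cohort (one suffices in the sentinel pair).

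**Days 3 and 4.** Subjects dose themselves at home (Section 8.2.1.2). Section 8.2.1.2.1.3 says: "No site visits are planned from Day 3 to Day 4". Table 1, footnote 8, adds: "Adverse events will be daily recorded by the subject in the subject diary and will not involve visit to the hospital". No call, remote check or time for diary review is given.

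**Day 5.** Section 8.2.1.2.2.1 has two lists. The first, "At Day 5, the following activities and assessments will be performed prior to IMP administration", names the urine pregnancy test and the PK sample. The second, "During Day 5, the following activities and assessments will be performed after IMP administration", names the examination, vital signs, laboratory tests, ECG, PK samples, concomitant medications and AEs.

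**Day 2.** Section 8.2.1.2.1.2 puts the assessments first and the dose afterwards: "and after the performance of the activities and assessments listed above), the subjects will be administered with the IMP". Section 10.3 says the reverse: "At Day 2, prior to all clinical activities and assessments and to hospital discharge, the subject will be administered with the IMP".

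**Sub-cohorts.** After a sentinel pair (one active, one placebo), Section 8.1 states: "The second sub-cohort will include 6 additional subjects simultaneously: 5 randomized subjects to receive ATL-001 and 1 to receive placebo".

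**The concern.** A pausing rule protects subjects only if qualifying events reach the site before the next dose. Here two of the four repeat doses are taken at home, and the next dose given at the site precedes the listed AE review. Outside the sentinel pair the grade criterion needs two subjects, so no single subject can know that it is met; someone at the site has to put separate diaries together.

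Two other provisions need the same information before the Day 5 dose. Section 9.4.2 names severe AEs and non-permitted medication as reasons to stop treatment, and Section 10.7 calls for a case-by-case decision when a dose has been missed. Collected after the Day 5 dose, the information comes when no IMP is left to withhold.

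The subjects are healthy volunteers, and gastrointestinal toxicity is the only risk identified in Table 2. The cohort review and the dose-limiting toxicity rule at FU-V1 still see the diary events. What is weakened is protection of the subjects already being dosed.

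**Working it through.** The plan gives no figure to reproduce. The check compares the schedule texts and then counts doses.

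**1. Do the tables supply the missing step?** No. Footnote 7, which marks pre-dose items repeated on Day 5, is attached only to the pregnancy test and PK rows in Protocol Table 1 and SAP Section 2.3.5. The pre-dose AE cell sits in the Baseline (Day 1) column of both tables. It carries footnote 9 (pre-treatment events) in Table 1 and footnote 8 (diary) in the SAP copy; neither makes it a Day 5 check. The first AE time point for Day 5 is 15 minutes after dosing.

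**2. Is Day 5 the exception?** Yes, within Section 8.2.1.2. Both of the other doses given at the site, on Days 1 and 2, have AEs listed before dosing there.

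**3. How long is the gap?** The Day 2 assessment is at 24 h. The Day 5 dose is nominally at 4 × 24 = 96 h. The gap is 96 − 24 = 72 h and spans the doses of Days 3, 4 and 5.

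**4. How many doses could follow an unseen trigger?** Inputs from Section 8.1: five daily doses; second sub-cohort 5 active + 1 placebo (6 × 5 = 30 doses); sentinel pair 1 active + 1 placebo (2 × 5 = 10 doses). The count is subjects × doses left. It assumes no report outside the diary and every dose taken, so these are upper bounds.

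| Criterion met after dose on | Doses left each | Second sub-cohort (active) | Sentinel pair (active) | Share removed by a Day 5 pre-dose check |
|---|---|---|---|---|
| Day 2 | 3 | 6 × 3 = 18 of 30 (5 × 3 = 15) | 2 × 3 = 6 of 10 (3) | 6/18 = 33% |
| Day 3 | 2 | 6 × 2 = 12 (10) | 2 × 2 = 4 (2) | 6/12 = 50% |
| Day 4 | 1 | 6 × 1 = 6 (5) | 2 × 1 = 2 (1) | 6/6 = 100% |

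The Day 5 check protects one dose per subject: 6 doses (5 active) in the second sub-cohort and 2 (1 active) in the sentinel pair. The remaining 18 − 6 = 12, 12 − 6 = 6 or 6 − 6 = 0 doses in the second sub-cohort depend on same-day reporting from home.

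**5. Day 2 order.** If Section 10.3 is followed, the 24-hour AE check comes after a further 6 × 1 = 6 doses (5 active) in the second sub-cohort, although subjects are then inpatients.

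**6. How likely is a trigger in the window?** The documents give no AE rate, so this is illustration only. Let p be an assumed per-subject probability of a qualifying grade 2 or higher AE in the window. For six subjects, P(at least 2) = 1 − (1 − p)^6 − 6p(1 − p)^5. For p = 5%, 10%, 20% and 30% this is 3.3%, 11.4%, 34.5% and 58.0%. For the sentinel pair, P(at least 1) = 1 − (1 − p)^2, which is 9.8%, 19.0%, 36.0% and 51.0%.

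**The case against.** The strongest reply is that AE capture is not confined to the visit lists. Section 12.2 requires careful monitoring throughout and covers anything a subject reports. Section 12.3 sets a 24-hour limit for serious events. Section 9.4.2 lets the subject or the investigator stop treatment at any time. Section 10.7 presupposes that the site hears of missed doses. The protocol also refers to instructions for home dosing and the diary that are not among these documents and may ask subjects to call. The subject is in the hospital on Day 5, and staff may well ask before dosing.

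Much of this stands as a limit on size. It is why the lower bound is zero and why the residual concern is mainly non-serious events that nobody reports. It does not supply a scheduled step. Section 12.2 names no time point, and its routine mechanism is the same diary. The 24-hour clock starts only when the site knows. An informal physician check at dosing cannot be assumed either, because Sections 8.1 and 10.2 require the responsible physician to be absent and Section 10.5 has an unblinded nurse give the IMP.

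Three further points are fair. The dose counts measure exposure rather than harm, and they include placebo. The Day 2 contradiction adds little to the pause argument, since AE checks run to 12 h on Day 1 with subjects in hospital. And Section 13.4 shows that Cohort 4 is complete, so the benefit now falls on Cohort 5: eight subjects, at the highest planned dose.

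**Conclusion.** The concern holds. As written, three of each subject's five doses (Days 3, 4 and 5) follow the Day 2 assessment with no scheduled AE review in between. On Day 5 the review is placed after the dose it should inform. The exposure at stake is at most 18 of 30 doses (15 active) in a second sub-cohort and 6 of 10 (3 active) in a sentinel pair. It falls to zero if subjects report promptly and the site acts. The upper figures assume diary-only capture and full dosing, and the documents do not allow an estimate of how likely that is. Sections 10.3 and 8.2.1.2.1.2 contradict each other on the Day 2 order whatever the event rates. The gap should be fixed; it does not undermine the escalation decisions or any analysis.

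**What to change.** 1. In Section 8.2.1.2.2.1, add AEs (with review of the diary, including doses taken) and concomitant medications to the list completed before the Day 5 dose, and keep AE recording after it. Extend footnote 7 to those two rows in Protocol Table 1 and SAP Section 2.3.5. This moves forward checks already made that day and takes a few minutes at admission.
2. In Section 8.2.1.2.1.3, ask subjects to report any new diary AE to the site the same day and before the next dose. The cost is occasional phone contact.
3. In Section 8.1.2, state that a pause includes telling subjects who hold IMP at home to stop. The cost is at most six calls, and only if a pause is triggered.
4. In Section 10.3, adopt the Day 2 order of Section 8.2.1.2.1.2: assessments, then dose. This is one sentence.

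Items 1 and 4 are the essential ones. Items 2 and 3 are small new procedures, but only they reach the Day 3 and Day 4 doses. Section 8.2.1 provides for changes in assessment timing to be documented in a Note to File, though it links such changes to a DSMB recommendation; items 2 to 4 probably need an amendment. No endpoint, sample size or pausing criterion changes: which events pause dosing stays as the sponsor defines it.
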